In Aim 1 of this study, we used input from stakeholder groups to inform development of a theory-based multicomponent behavioral intervention for older Veterans with cLBP and depression—the intervention (Aim 1 in the attached CDA-2 Research Plan). In Aim 2 we conducted preliminary testing of the intervention in a sample of 7 Veterans with the purpose of evaluating procedures for the recruitment process, enrollment, usability of manuals, fidelity ratings, and study procedure. In Aim 3, will we assess the feasibility for older Veterans with cLBP and depression assigned to receive the behavioral intervention (n=25) versus the waitlist control (n=25). Follow-up will also include assessments at 6 months and 12 months post-intervention. In the Annie texting pilot, up to five Veterans who have completed MOTIVATE will be asked to provide feedback on the usability and understandability of the proposed texting system. After this, the feasibility of the texting program will be tested in a small group of Veterans who have completed MOTIVATE (n=7-10). This will be followed by in-depth semi-structured interviews to gather more information about barriers and facilitators of using the texting program to capture data on steps, mood and pain.

Figure 3. Overview of Aim 3 Pilot RCT and Assessment Intervals

Overview of Proposed intervention: The behavioral intervention is designed for older Veterans with cLBP and depression and will include 8 individual telephone sessions delivered by health coaches over a period of 10-20 weeks (up to 5 months total, accounting for additional time between sessions if needed). Based on what we learned from Aim 2, we will allow an additional week or two weeks between sessions (if 1 week scheduled between sessions, we will allow one additional week for scheduling; if 2 weeks allowed we will allow up to 4 weeks); prolonging the time between sessions will be at the discretion of the PI and research team. Exceptions may be made for highly motivated subjects who had unfortunate life circumstances arise.

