- Comorbidities will be obtained from CPRS, prior to baseline, using the previously validated self-report version of the Charlson index;
- Substance use will evaluate for alcohol abuse (Short Michigan Alcoholism Screening Test), and illicit substance use (Drug Use Questionnaire [DAST-10] that was found previously to negatively impact outcomes;
- Mild cognitive impairment (MCI) - subjects not excluded based on the telephone Memory Impairment Screen will be screened for the presence of MCI with a Six-Item Screener. Prior research demonstrates that cognitive function mediates the relationship between pain and physical performance in older adults with cLBP. This may also impact adherence to behavioral interventions;
- Future Time Perspective scale consists of 10 statements about the subjective perceptions of time and is most commonly used to assess time horizons;
- Medications (see below for more details);
- Body mass index will be obtained from CPRS; Self-report of pain, physical/psychological/social function, quality of life (see primary/secondary outcomes).
- Sleep: PROMIS SF 6-item questionnaire to assess sleep
- Resilience: Connor Davidson Resilience Short Form: CDRISC 10 item that assesses resilience
- Patient Satisfaction Survey – six questions about the subject's experience in the study that will be asked at the end assessment
- Texting response rates of Veterans via Annie dashboard.
- Trends of step counts, pain scores, and mood scores overtime via the Annie texting dashboard
- Patient satisfaction survey among Annie texting pilot - questions on the about the subject's experience will be asked at the end of the assessment

Primary Feasibility Outcome Measures in Aim 3: Feasibility outcomes will be useful for the planning a hybrid effectiveness/implementation merit IIR award. These outcomes include: enrollment rates across different primary care clinics at Dallas VAMC; intervention adherence (measured as number of sessions the subject engaged in) and retention; use trends of Annie texting over time.

Upon completion of the intervention, a member of the research team (not the individual conducting the intervention sessions) will conduct in-depth semi-structured interviews and will also seek ratings of the helpfulness of skills taught (Likert scale), overall satisfaction, and whether the information presented provided appropriate motivation to continue practicing learned skills. The data collected from these

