Proposed Analyses: Exact binomial method will be used to estimate rates of recruitment, intervention adherence, retention, and drop-out along with the corresponding 95% confidence intervals. Multiple levels of treatment retention will be defined, including partial intervention completion (% who do not complete all sessions), intervention dropout (% who dropout of intervention but continue to do assessments), research dropouts (% who remain in intervention, but do not complete assessments), and intervention + research dropouts (% who do not complete intervention or assessments). We will further break down the enrollment and retention calculations by examining enrollment/retention differences by treatment group, health coach, gender, age, race/ethnicity, and initial cLBP and depression severity using cross-classification tables.

As exploratory analyses, pre-post improvement in disability (RMDQ) and depression (PHQ-9) scores, as well as secondary and intermediate outcomes, from baseline to 3 months will be compared based on a two-sample t-test or Wilcoxon rank-sum tests between the two groups. The difference in improvement will be estimated and the 95% confidence interval will be reported. We will estimate the preliminary effect size and variance of effect for the above outcomes. Linear mixed models will be used to assess whether there is a difference in the above outcomes over time within and between the two groups. We will include distance (in miles) from a VA facility as a covariate in the exploratory outcome analyses, as suggested by reviewer.

We will describe, for the subset of subjects receiving the intervention, whether physical activity (proximal outcome) and clinical outcomes (disability and depression scores) change over time based on the 1) proportion of the total sessions completed, and 2) the proportion of individual sessions completed. This will help us estimate optimal dose of the intervention (for example, whether completion of 4 vs. 7 vs. 8 of 10 sessions produces similar outcomes) and may inform which specific sessions are absolutely critical. SAS (version 9.3, Cary, NC) statistical software will be used.

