Our formative evaluation may help to identify parts of the process that need refinement to maximize the feasibility and extension of the project to different sites (in anticipation of the IIR proposals). Also, part of the formative evaluation process will be to understand how implementation factors influence the optimal dose of our intervention. This evaluation may highlight which intervention components (or active ingredients) resulted in a change in behavior or other outcome result and potentially why (barriers/facilitators of change from an implementation standpoint).

Analyses for the Annie-texting pilot: Phase 1: these qualitative and interview data will be used to inform

consent and procedure development for Phase 2. No formal analytic methods will be used. Phase 2: feasibility will be assessed by looking at response rates through the Annie dashboard. At the end of phase 2, semi-structured interviews will take place among the participants regarding their opinions, barriers, and thoughts for improvement of the Annie texting system as tool to assist in pain management.

14. Provisions for Managing Adverse Reactions

We do not anticipate any adverse reactions as this study only involves interviews; hence, there is minimal risk of physical injury.

As part of the Annie texting pilot, we will develop orientation materials introducing the VA Annie texting system, which includes statements regarding safety and who to contact for questions or concerns. The Annie dashboard will be monitored twice/ week by the MOTIVATE research team for any concerning texts that may prompt a phone call for escalating symptoms. Similarly, if a subject persistently does not respond to any of the Annie text prompts, the research team will call the Veteran for a check-in and to trouble shoot any issues with technology.

15. Risk/Benefit Assessment

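### Adherence is defined as a per-subject session count but assigned an exact binomial, and non-randomised attendance is said to help estimate the optimal dose and identify critical sessions

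*Combined protocol and SAP*

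**What the plan says.** **Adherence.** Section 13, Primary Feasibility Outcome Measures in Aim 3, lists "intervention adherence (measured as number of sessions the subject engaged in) and retention" among the outcomes meant for planning the next award. Under Proposed Analyses in the same section: "Exact binomial method will be used to estimate rates of recruitment, intervention adherence, retention, and drop-out along with the corresponding 95% confidence intervals". No rule turns the count into adherent or not adherent, and the binomial unit (subject or session) is not stated. The only session-based yes/no item is "partial intervention completion (% who do not complete all sessions"), which is listed as a level of treatment retention.

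**Session total.** Section 11 gives 8 telephone sessions. Section 12 gives 8 modules plus 3 check-in calls, and later 11 in total. The dose example in Section 13 compares 4, 7 and 8 sessions out of 10.

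**Dose.** Proposed Analyses will describe, among intervention recipients only, whether physical activity, disability and depression change according to the share of sessions completed, overall and by individual session. It continues: "This will help us estimate optimal dose of the intervention", and it "may inform which specific sessions are absolutely critical". No caveat about who attends is given.

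**The concern.** The measure and the method do not match. Two analysts following the text could report different adherence results from the same data: one might dichotomise at a cut-off of their own, another might report completion of all sessions, and neither result would be the stated outcome. A trial planned from this pilot would then lack the quantity that the protocol chose to measure, namely how many sessions subjects take up and how uncertain that figure is.

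The dose wording goes beyond what the design can deliver. Only arm is randomised; the number of sessions taken is settled afterwards, by or for each subject. Subjects who attend more may have done better anyway. If the comparison is read as a dose estimate, the next trial could drop or keep sessions because of a difference that selection alone can produce.

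**Working it through.** The plan states no expected adherence, precision or power, so there is no figure of its own to reproduce. From the documents: 25 intervention subjects (Sections 9 and 12) and 8 modules (Sections 11 and 12). Everything marked assumed is illustrative.

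**1. Completion does not stand in for the count.**
- A mean of 6 of 8 (assumed) is 25 × 6 = 150 sessions.
- Fewest completers: all 25 attend exactly 6, giving 0.
- Most completers: floor(150/8) = 18, or 18/25 = 72%; the other 7 subjects share the remaining 150 − 144 = 6 sessions.
- The same mean therefore fits 0% to 72% completing.
- The exact binomial does suit completion itself: 15/25 (assumed) = 60%, Clopper-Pearson 95% CI 38.7% to 78.9%.

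**2. A cut-off changes the answer.** Take hypothetical counts for 25 subjects: twelve 8s, four 7s, three 6s, three 4s, two 2s and one 0 (mean 158/25 = 6.32). The adherent share is
- 22/25 = 88% at 4 or more sessions;
- 19/25 = 76% at 6 or more;
- 16/25 = 64% at 7 or more;
- 12/25 = 48% at all 8.

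**3. What a per-subject interval gives.** With mean proportion p = 0.75 (assumed) and within-subject correlation ICC (assumed), the 95% interval is p ± t(24) × sqrt[p(1 − p)(1 + 7 × ICC)/200], where t(24) = 2.064.
- ICC 0.2: 65.2% to 84.8% (half-width 0.78 sessions).
- ICC 0.5: 61.6% to 88.4% (1.07 sessions).
- ICC 0.8: 58.8% to 91.2% (1.30 sessions).

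Beta-binomial simulation (25 subjects × 8 sessions, 40,000 runs, ICC 0.2 to 0.8) gave this coverage:
- 75% attendance: t interval about 94%.
- 90% attendance: t interval 89% to 91%; logit-scale interval 92% to 95%.
- 95% attendance with ICC of 0.5 or more: neither is adequate (75% to 87%).

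**4. The denominator.** 8 + 3 = 11, so the totals of 8 and 11 agree once check-in calls are recognised; 10 fits neither. Eight sessions is 100% of 8, 80% of 10 and 73% of 11.

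**5. Dose difference from selection alone.** Let attendance propensity be normal, with the top share q completing, and let it correlate r with improvement, with no session effect. Completers then exceed the rest by r × φ(z)/[q(1 − q)] SD, where z is the normal quantile at q. With q = 0.60 (assumed), φ(z) = 0.3863 and 0.3863/0.24 = 1.610.
- r = 0.1: 0.16 SD.
- r = 0.3: 0.48 SD.
- r = 0.5: 0.80 SD.

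**6. Precision.** The half-width of a 95% CI for a difference, in SD units, is t(23) × sqrt(1/n1 + 1/n2), with t(23) = 2.069.
- 15 v 10: 2.069 × 0.408 = 0.84.
- A session missed by 6 of 25 (19 v 6): 0.97.
- A session missed by 3 of 25 (22 v 3): 1.27.

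An interval that wide cannot establish that two attendance levels give similar outcomes.

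**The case against.** The strongest reply is that this is a feasibility pilot of 25 per arm, that both points are matters of wording, and that a one-line rule for who counts as adherent would make the exact binomial valid. The last part is correct, and the exact binomial already suits enrolment, retention and completion. But a cut-off replaces the stated outcome with another one, and step 2 shows how far the result depends on it. The dose paragraph is also presented as description, follows analyses labelled exploratory, sets no test or decision rule, and hedges the remark on critical sessions. That limits the harm, but the optimal-dose sentence carries no caveat about self-selection.

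Four stronger readings are tempting and are not supported:
- *Sessions will be pooled as 200 independent trials.* Nothing in the documents says so. Pooling is something to rule out, not an error the plan has made.
- *The formative evaluation makes the same inference from attendance.* It does speak of "how implementation factors influence the optimal dose of our intervention" and of "which intervention components (or active ingredients) resulted in a change in behavior or other outcome result". Section 13 ties that evaluation to semi-structured interviews, and the second statement is given only as something it may highlight. The self-selection argument is not shown to apply there.
- *The protocol itself links attendance to prognosis.* "Exceptions may be made for highly motivated subjects who had unfortunate life circumstances arise" concerns the time allowed between sessions, and the conceptual model in Section 6 treats motivation as a target of the intervention. Neither says that better attenders have better outcomes. The concern rests on attendance not being randomised.
- *The session totals conflict throughout.* Only the total of 10 fails to fit.

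**Conclusion.** Both points stand as limited but real defects of the analysis section.

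The adherence mismatch follows from the text and needs no assumption about attendance. Its consequence is that the stated method cannot report the stated outcome, and completion is no substitute (0 to 18 completers at the same assumed mean).

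The dose inference is not supported by a non-randomised comparison within one arm. The 0.16 to 0.80 SD range shows what selection can do under an assumed 60% completing and assumed correlations of 0.1 to 0.5; it does not predict the bias in this trial. The 0.84 SD half-width depends only on an assumed 15 v 10 split and equal SDs. Because the comparison is exploratory, what is at risk is interpretation and carry-over to the next trial, not a confirmatory error rate.

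**What to change.** **Adherence.** Report the number and proportion of sessions per subject, with the full distribution and a 95% CI computed over the 25 intervention subjects: a t interval, or the logit scale when attendance is about 90% or more. If attendance is close to 100%, rely on the distribution and the exact CI for completers. Keep the exact binomial for the proportion completing all sessions. State that pooled sessions will not be treated as independent.

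**Denominator.** State whether the 3 check-in calls count as sessions, and reconcile the total of 10 in the Section 13 dose example with the 8 modules and 3 check-ins (11) in Sections 11 and 12.

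**Dose.** Keep the analysis by sessions completed as a descriptive, hypothesis-generating association, and remove the optimal-dose and critical-session inference from that paragraph of Proposed Analyses. The formative-evaluation paragraph need not change on this account.

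**Cost.** Wording and one decision on the denominator, with no new data. The downsides are an adherence interval that is only approximate when attendance is very high, and a more modest statement about dose.

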criteria for age and cLBP will receive an opt-out letter about the study (included as a supplemental file, will be signed by PRIME or ambulatory care director, as appropriate). The *second* method involves: identifying when potentially eligible participants have appointments in a primary care clinic (including both PRIME and ambulatory care clinics), or specialty clinic such as Rheumatology or PM&R. The provider will introduce the study and research staff to the Veteran in person. The research staff will then describe the study and obtain consent if subject is interested. Additionally, the *third* recruitment strategy involves referral directly from a provider. [name] will provide a flyer to be posted in PRIME or ambulatory care clinics (see attached to this IRB protocol submission) outlining the eligibility criteria and brief synopsis of the study. If the Veteran is interested in learning more and participating in this study, he or she may call [name] or the study team at the number provided on the flyer, or, with the HIPAA waiver, the provider may notify [name] team to call the Veteran (as additional cosigner on the clinic note). When/if [name] or her research team speaks with the Veteran (preferably in person but may be over the telephone if more convenient for the Veteran), we will describe the study, risks and potential benefits and obtain consent, also for audio-recording. The eligibility criteria will be assessed and confirmed over the phone or in person (whichever more convenient for Veteran) via self-report and review of CPRS data. If consent is obtained in person, the forms will be signed then. If the discussion occurs over the phone and the Veteran agrees to participate in this study, a consent form, HIPAA authorization and audio-recording consent form will be mailed to the Veterans home. He or she will sign the consent (without social security number) and return via mail or bring the signed forms in person at the time of the in-depth interview.

Inclusion Criteria:

- Men and women Veterans aged 65+
- English- speaking
- Self-reported low back pain (+/-radiation) on most days for the past 3 months, that interferes with daily activities. Low back pain interferes with daily activities, assessed with the question "does your back pain limit your ability to do activities around the home or activities that you enjoy?"
- Chronic low back pain with intensity of 4 or higher on 10 point scale

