The **third** recruitment strategy involves referral directly from a provider. [name] will provide a flyer to be posted in PRIME, ambulatory care, Rheumatology or PM&R clinics (see attached to this IRB protocol submission) outlining the eligibility criteria and brief synopsis of the study. If the Veteran is interested in learning more and participating in this study, he or she may call [name] or the study team at the number provider on the flyer, or, with the HIPAA waiver, the provider may notify [name] to call the Veteran (as additional cosigner on the clinic note). When/if [name] or her research team speaks with the Veteran (preferably in person but may be over the telephone if more convenient for the Veteran), we will describe the study, risks and potential benefits and obtain consent, also for audio-recording. The eligibility criteria will be assessed and confirmed over the phone or in person (whichever more convenient for Veteran) via self-report and review of CPRS data.

The inclusion and exclusion criteria (listed in detail in section 8) that will be assessed via the telephone or in person depending on recruitment method with a combination of self-reported measures, survey, and by review

of electronic medical record data. Veterans receiving mental health services at the time of the study recruitment will not be excluded. All mental health treatments and health service-use characteristics will be included in the study analyses as covariates. Verification of cLBP will be based on the self-report to questions listed in the eligibility screener (provided as supplemental document). Depression criteria will be based on participant self-report of clinically significant depressive symptoms according to the PHQ-9 (in person or via telephone screening). We will use the established cut-off score of ≥ 10 on the PHQ-9 to signify a clinically meaningful symptom burden. If the Veteran is not already enrolled in mental health clinic and scores ≥ 10 on PHQ-9, we will send the PCP a message in CPRS notifying him/her and suggesting further discussion about referral to mental health.

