A protocol will be in place should the study team identify a potential participant who reports or develops suicidal ideation. For safety purposes, the protocol is as follows: Any patient identified as having suicidal ideation during this screening process will be referred to [name] and will be referred to the VA suicide hotline that involves warm transfers to mental health professionals. Using a pre-established protocol, [name] will contact the subject and make arrangements for immediate mental health assessment and treatment based on the subject's symptoms. All suicidal patients will be provided with the VA suicide crisis hotline number, regardless of other immediate clinical interventions. Furthermore, subjects with severe psychiatric diagnoses (as specified among the exclusion criteria) or prior documented inpatient admissions for suicidal ideation will be excluded and not enrolled in the study.

Randomization: Once the baseline assessment has been completed, eligible participants will be randomly assigned to the waitlist control group (n=25) or the intervention (n=25) by applying a set of computer-generated random numbers. Since we are interested in better understanding feasibility of the intervention as compared to the waitlist control, and how behaviors are sustained over time, Aim 3 involves extended follow-up to 12-months. We will use these extended follow-up data to better understand differential attrition as well as preliminary formative implementation evaluation (see below).

At this time, a binder with the intervention manual material will be sent to the subject's home if randomized to the intervention arm. This manual is intended for the patient to follow along with the health coach during phone calls. It will also contain the activity trackers that he/she will use in between session to track activity, step counts, and impact on pain and depression.

We will mail out appointment letters before each intervention visit. Depending on the content of the session, these reminders may also include a list of the subject's values, goals and action plan. The patients will also be called by a research team member or the health coach prior to the scheduled phone calls as a reminder. During Aim 2, we learned that some patients are forgetful about the timing of the phone calls which causes delays-these phone call reminders were helpful.

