Timing of assessments/ data collection: The research staff will screen, identify eligible Veterans for the study, obtain consent (either in person or verbally (over the phone) initially followed by mailed written consent), and complete further screening for eligibility. If the subject is eligible for this study, the research staff will arrange a separate phone call for a baseline assessment via telephone. The baseline interview must be completed within 2 weeks for the participants to proceed to the intervention. This time frame may be extended at the discretion of the study team. Once the baseline visit is complete then the patient will be informed if randomization allocation.

As seen in the Figure below, the health coaches will conduct the once a week session (or every two weeks depending on the session content) sessions (11 in total), delivered via telephone. A research team member, not the individual conducting the intervention sessions, will complete all assessments via telephone using a structured data collections tool at baseline, 5 weeks (mid-point assessment), at 10 weeks (post intervention

session), 6 months and 12 months post-intervention. Those in the Annie texting-pilot will participate for the duration that the MOTIVATE sessions are typically provide to the waitlist control group (8 sessions over 12-20 weeks). The study team will also conduct interviews as outlined above at 6 months and 12 months to obtain feedback regarding implementation and sustainability of the behaviors learned. The data from these assessments will be entered into a VA Redcap database <https://vhacdwweb05.vha.med.va.gov/> that is housed behind the VA firewall on secure research folder on VA servers:

<\\v17.med.va.gov\\v17NTX\\Services\\Research\\[name]-Research>. All data entered into Redcap is de-identified. Following the physical activity session, the health coach or research staff will obtain daily versus weekly step counts that the subject will read out over the phone. Total steps taken will be documented within 1 week, and then at during subsequent health coaching sessions as well as the 10 week assessment by research staff.

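### The exploratory RMDQ and PHQ-9 arm differences come from change scores with no baseline term; adjusting for the baseline score would usually tighten the intervals at no data cost

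*Combined protocol and SAP*

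**What the plan says.** All of this is in the combined protocol and SAP.

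- **Arm comparison.** Section 13, Proposed Analyses: improvement in RMDQ, PHQ-9 and the other scores listed there "from baseline to 3 months will be compared based on a two-sample t-test or Wilcoxon rank-sum tests between the two groups". A 95% CI accompanies the estimated difference, and the plan adds: "We will estimate the preliminary effect size and variance of effect for the above outcomes".
- **Mixed models.** Same paragraph: "Linear mixed models will be used to assess whether there is a difference in the above outcomes over time within and between the two groups". Whether baseline is a response, a covariate or a common mean is not stated.
- **Covariates.** Same paragraph: "We will include distance (in miles) from a VA facility as a covariate in the exploratory outcome analyses". Sections 8 and 12 add mental-health treatment and service use. No section names the baseline score.
- **Timing of baseline.** Section 12, Randomization: "Once the baseline assessment has been completed, eligible participants will be randomly assigned to the waitlist control group". Section 12, Timing of assessments, adds that for eligible subjects "the research staff will arrange a separate phone call for a baseline assessment via telephone".
- **Entry limits.** Section 12: "Depression criteria will be based on participant self-report of clinically significant depressive symptoms according to the PHQ-9 (in person or via telephone screening"), with a cut-off of 10 or more. Section 8 also requires "Chronic low back pain with intensity of 4 or higher on 10 point scale", and back pain that interferes with daily activities.
- **Status.** These analyses are labelled exploratory. The primary outcomes are feasibility measures, and RMDQ and PHQ-9 are listed as primary outcomes for a future effectiveness trial.

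**The concern.** A change score subtracts the whole baseline value, which amounts to fixing the slope of follow-up on baseline at 1. ANCOVA estimates that slope. When the slope is below 1, as regression to the mean usually makes it, the change score carries baseline noise that the analysis could remove. The baseline value is already collected before allocation, so adjusting for it is valid and needs no new data.

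There is also an internal gap. The plan promises distance as a covariate in the exploratory outcome analyses, but neither a two-sample t-test nor a rank-sum test can carry a covariate. Of the planned methods, only the mixed models can keep that promise.

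What is at stake is the precision of a preliminary effect and its variance, estimated from 25 per arm. The planning of the later trial would be the natural user of both.

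**Working it through.** **No figure to reproduce.** The documents give no SD, effect size, power or correlation for RMDQ or PHQ-9.

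**Inputs.** From the documents: 25 per arm and a 95% CI. Assumed: in-trial baseline/follow-up correlation ρ of 0.5, 0.6, 0.7; ratio k = baseline SD / follow-up SD of 1.0, 0.9, 0.8, 0.7. Widths are in follow-up SD units.

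**Formulas (n = 25 per arm).**
- Change score half-width: t(0.975, 48) × √[2(1 + k² − 2ρk)/n], with t = 2.0106.
- ANCOVA half-width: t(0.975, 47) × √[2(1 − ρ²)/n × (1 + 1/46)], with t = 2.0117. The last factor, 47/46 = 1.022, is the price of estimating the slope.

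**Worked case, k = 1, ρ = 0.5.** Change score: 2.0106 × √(2 × 1.00/25) = 0.569. ANCOVA: 2.0117 × √(2 × 0.75/25 × 1.022) = 0.498. Ratio 0.876, so 12% narrower.

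**ANCOVA / change-score CI width:**

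| k | ρ = 0.5 | ρ = 0.6 | ρ = 0.7 |
|---|---|---|---|
| 1.0 | 0.876 | 0.905 | 0.932 |
| 0.9 | 0.918 | 0.947 | 0.974 |
| 0.8 | 0.956 | 0.981 | 1.002 |
| 0.7 | 0.985 | 1.004 | 1.011 |

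At k = 1 the large-sample variance ratio is (1 + ρ)/2 = 0.75, 0.80, 0.85. That is worth 25/(ratio × 1.022) = 32.6, 30.6, 28.8 per arm. The gain disappears when ρ = k, where the slope is exactly 1.

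**Simulation check** (normal data, 4,000 trials per setting). Mean width ratios were 0.876 and 0.933 at k = 1 for ρ = 0.5 and 0.7, and 0.985 and 1.011 at k = 0.7. ANCOVA gave the narrower interval in 98%, 90%, 59% and 21% of trials respectively.

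**Dropout.** With 20 analysed per arm (assumed), the k = 1 ratios are 0.879, 0.908, 0.936. The least favourable cell, k = 0.7 and ρ = 0.7, becomes 1.015.

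**Mixed models.** For five complete visits, known covariance, equal SDs and ρ = 0.5, 0.6, 0.7 between baseline and 10 weeks:
- Free arm-by-visit terms: SE 0.2828, 0.2530, 0.2191, which equals the change score, √[4(1 − ρ)/25].
- Baseline constrained equal across arms: SE 0.2449, 0.2263, 0.2020, which equals ANCOVA, √[2(1 − ρ²)/25].

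**Which correlation is meant.** Selection on a score lowers its SD and its correlation with follow-up together. Suppose selection acts on the baseline score itself and leaves a fraction v of its variance. A pre-selection correlation r then becomes r√v / √(1 − r² + r²v) in the trial. With v = 0.5, r = 0.7: 0.495/0.869 = 0.57. With v = 0.36, r = 0.5: 0.300/0.917 = 0.33. On this pre-selection scale, r = 0.5-0.7 gives CIs 2-6% narrower, and ANCOVA loses only above r = 0.88-0.91. If PHQ-9 screening and baseline are separate measurements correlated 0.7-0.9 (assumed), simulation on the same scale gives 3-10% narrower. These figures must not be read against the in-trial correlation used in the table.

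**The case against.** **The mixed models may already do this.** They may: baseline as a covariate, or constrained equal across arms, recovers the precision. The text does not say so, and the obvious free arm-by-visit model with complete data does not recover it. A reader might infer that every exploratory analysis ignores baseline. The documents support only that the t-test or Wilcoxon comparison has no baseline term and that its handling in the mixed models is unstated.

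**Adjustment need not narrow the interval.** This stands. PHQ-9 entry at 10 or more may shrink the baseline SD, and the table shows ratios of 1.00 to 1.01 at ρ = 0.6-0.7 in some cells. RMDQ has no numeric cut-off, but the entry rules on pain interference and intensity may restrict it somewhat, so k = 1 is its favourable case. PEG could be affected likewise. Against this, ρ = 0.7 with k = 0.7 implies a slope of 1, meaning no regression to the mean. Selection alone does not produce that, because it leaves the slope unchanged.

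**Nothing turns on it.** Also largely true. No decision rule depends on these intervals.

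**Is the planned analysis invalid?** A reader might infer that change scores bias the comparison. Randomisation makes the change-score difference unbiased; simulated means for both methods, with selection modelled, were -0.493 to -0.508 against a true -0.50.

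**Conclusion.** The point holds as a free improvement to the exploratory analyses, not as an error in the trial's primary analysis. Under an assumed in-trial correlation of 0.5-0.7 and 25 per arm, baseline adjustment narrows the CI by about 7-12% with equal SDs and about 3-8% at an SD ratio of 0.9. At a ratio of 0.7-0.8 it runs from about 4% narrower to 1% wider. RMDQ probably gains more than PHQ-9. The correlation and both SDs are assumptions, so a guaranteed gain for every score cannot be claimed. The mismatch between the promised distance covariate and tests that cannot carry one does not depend on these assumptions.

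**What to change.** - **Estimate.** Report the arm difference and 95% CI from ANCOVA: follow-up score on arm, pre-randomisation baseline score and the promised distance. Alternatively, use the planned mixed model with arm-by-visit terms and baseline either as a covariate or constrained equal across arms. A rank test can stay as a sensitivity analysis.
- **Scope.** Apply this only to measures with a value before randomisation. Exclude therapeutic alliance (first taken at 5 weeks) and global impression of change. Exclude step counts too unless they are collected before randomisation, since Section 11 mails the pedometer between sessions 1 and 2.
- **Visit.** Name the follow-up assessment. Proposed Analyses says 3 months, while Section 12 schedules 5 weeks, 10 weeks, 6 months and 12 months.
- **Reporting.** Give the SD at each visit and the baseline/follow-up correlation alongside the effect size.

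The cost is a change of analysis wording and one degree of freedom for baseline, at most about 1-2% of CI width in unfavourable cases. Distance is already the plan's own commitment and is not counted in that cost.
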